1. BACKGROUND

1.1 Disease

Meibomian gland dysfunction (MGD) is a chronic condition and the main cause of dry eye disease (DED) nowadays. [1-2] It affects the meibomian glands, leading to blockage of the ducts and changes in the secretion of oil. This can result in issues with the tear film, eye irritation, inflammation, and ocular surface disease. [1]

MGD can cause various eyelid symptoms, including prominent blood vessels, frothy discharge along the eyelid margin, blocked meibomian glands, and thickened or irregular eyelid margins. Patients with MGD often have rosacea or seborrheic dermatitis. MGD can lead to reduced availability of normal oil on the eyelid and tear film, resulting in increased tear film instability, bacterial growth, evaporative dry eye, and inflammation of the ocular surface. [1-2]

1.2 Current therapeutic options

The patient should understand that a complete cure is usually not possible for blepharitis. As a matter of fact, the main goal of the treatment is the control of the ocular symptoms in the majority of the cases. The main treatments for MGD are:

- Warm compresses
- Eyelid cleansing and massage to express the meibomian glands
- Antibiotics (topical and/or systemic)
- Topical anti-inflammatory agents (e.g., corticosteroids, cyclosporine)

These treatment options are often used in combination. The optimal treatment regimen often requires persistence and a trial-and-error approach.

An initial step in treating MGD patients is to recommend warm compresses and eyelid cleansing with the addition of ocular lubricants. For patients with MGD, whose chronic symptoms and signs are not adequately controlled with the previous approach, oral tetracyclines and topical antibiotics may be helpful. Doxycycline, minocycline, or tetracycline can be given daily and tapered after clinical improvement is noted. Alternatively, oral erythromycin or azithromycin can be used, especially in women of childbearing age and children. [1-2]

1.3 Devices under study

The drug in the study is oral doxycycline, which is the most commonly used oral tetracycline for treating posterior blepharitis and MGD. The rationale for using tetracyclines is based in part on small clinical trials that have reported the drugs' effectiveness in improving symptoms in patients with ocular rosacea and in improving tear break-up time in patients with rosacea and MGD. [1]

Doxycycline is a metal ion chelator and a broad-spectrum antibiotic that prevents access of acyl t-RNA to the acceptor site on the mRNA-30s ribosomal subunit complex. In addition to these established functions, other properties that have recently been ascribed to

Clinical Trial Protocol CPDOXY1

Comparison between continuous and pulsed oral doxycycline treatment protocols for refractory meibomian gland dysfunction - 9 months follow-up prospective study

doxycycline include differential inhibition of the activity of members of the matrix metalloproteinase (MMP) family, inhibition of MMP synthesis, inhibition of interleukin-1 synthesis, inhibition of activated B cell function, inhibition of nitric oxide (NO) synthesis by lipopolysaccharide activated macrophages, and inhibition of collagen synthesis by cultured chondrocytes. [3]

Tetracyclines also decrease lipase production in both *S. epidermidis* and *S. aureus*. However, it's worth noting that tetracyclines can cause photosensitization, gastrointestinal upset, vaginitis, and, rarely, azotemia. Tetracyclines have been implicated in cases of pseudotumor cerebri, and their metabolism may alter the effectiveness of certain medications (e.g., decrease the effectiveness of oral contraceptives and potentiate the effect of warfarin). Tetracyclines are contraindicated in pregnancy, for nursing women, and for patients with a history of hypersensitivity to tetracyclines. Furthermore, tetracyclines should not be used in children under 8 years of age since staining of teeth may occur; however, oral erythromycin may be used as an alternative. [1-2-3]

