6.2 Inclusion criteria

- 18 years or older
- provided written informed consent
- OSDI score of 13 or more at the baseline visit after at least two months of first-line therapy (artificial tears and warm compresses)
- Clinical diagnosis of MGD
- Type 1 Schirmer test > 10 mm
- No previous history of allergy or sensitivity to doxycycline,
- No use of additional topical or systemic antibiotics for the prior 2 months
- No use of topical anti-inflammatory agents (ex: corticosteroids or cyclosporine) for the prior 3 months.

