6.3 Exclusion criteria

- Active ocular inflammation in either eye,
- Demodex blepharitis,
- Ocular surgery within the past 3 months of baseline examination,

Clinical Trial Protocol CPDOXY1

Comparison between continuous and pulsed oral doxycycline treatment protocols for refractory meibomian gland dysfunction - 9 months follow-up prospective study

- Structural ocular surface and eyelid abnormalities.
- Sjögren's syndrome
- Rheumatoid arthritis
- Other systemic diseases resulting in dry eye
- Known autoimmune disease
- Doxycycline allergy or sensitivity
- History of antibiotic therapy at any time within 2 months of the commencement of study
- Use of significant calcium supplementation or other medications that could interfere with doxycycline absorption (es: Iron supplementation)

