7. STUDY TREATMENT

7.1 Study supplies

Study treatment will be prescribed to the patient as for normal clinical practice

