14.7 Study timetable and end of study

	Visit 1 (day 0)	Visit 2 (day 90)	Visit 3 (day 180)
Verify inclusion and exclusion criteria	X		
Informed consent signature	X		
OSDI questionnaire	X	X	X
NIBUT	X	X	X
AS assessment of blepharitis and hyperemia	X	X	X
TBUT	X	X	X
Adherence to study treatments		X	
Prescribe study drug	X		

Clinical Trial Protocol CPDOXY1

Comparison between continuous and pulsed oral doxycycline treatment protocols for refractory meibomian gland dysfunction - 9 months follow-up prospective study

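### The protocol calls tetracyclines contraindicated in pregnancy and nursing, yet no eligibility criterion excludes pregnant or nursing women

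*Protocol*

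**What the plan says.** Section 1.3 identifies the study drug as oral doxycycline, a member of the tetracycline class, and states the class contraindications: "Tetracyclines are contraindicated in pregnancy, for nursing women, and for patients with a history of hypersensitivity to tetracyclines". It adds a separate age warning: "tetracyclines should not be used in children under 8 years of age since staining of teeth may occur".

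Eligibility is set in two lists:

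- Section 6.2 (inclusion) contains the age limit, "18 years or older", and the allergy condition, "No previous history of allergy or sensitivity to doxycycline".
- Section 6.3 (exclusion) repeats the allergy condition as "Doxycycline allergy or sensitivity".

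The schedule in 14.7 gives Visit 1 one row for checking eligibility, "Verify inclusion and exclusion criteria", and another for "Prescribe study drug". On supply, section 7.1 says: "Study treatment will be prescribed to the patient as for normal clinical practice".

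**The concern.** Section 1.3 names pregnancy, nursing and hypersensitivity in one sentence. Only hypersensitivity was turned into an eligibility rule. Pregnancy and nursing stop at the background section.

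The scheduled eligibility check can only test what 6.2 and 6.3 list. Applied exactly as written, it would pass a pregnant or nursing adult with refractory MGD, who would then be prescribed a drug from a class the protocol says she should not receive. Under 7.3 the drug is taken at home for three months, and both arms contain it, so neither allocation avoids the exposure.

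The harm at stake falls on a fetus or a nursing infant. Section 10.6 includes fetal harm and birth defects among serious adverse events. That is standard wording and does not suggest that exposure is expected. It does mean that such harm would be recorded once it had happened, while no written criterion stops the exposure beforehand.

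**Working it through.** There is no figure in the plan to reproduce here. The check is a count and a side-by-side reading of 1.3, 6.2, 6.3 and 14.7.

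**Step 1. Count the criteria and look for pregnancy or nursing.**

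- Section 6.2 has 8 items: age; consent; OSDI threshold after first-line therapy; MGD diagnosis; Schirmer result; no doxycycline allergy; no recent antibiotics; no recent topical anti-inflammatory agents.
- Section 6.3 has 11 items: active ocular inflammation; Demodex; recent eye surgery; structural abnormalities; Sjögren's syndrome; rheumatoid arthritis; other systemic causes of dry eye; autoimmune disease; doxycycline allergy; recent antibiotics; calcium or other products affecting absorption.
- Total: 8 + 11 = 19. Items mentioning pregnancy or nursing: 0 of 19.

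**Step 2. Ask whether any item excludes these women indirectly.** None does by design. There is no restriction on sex, no upper age limit and no condition on childbearing status. The calcium and iron item concerns drug absorption, so it would remove a pregnant woman only if she happened to take such a product.

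**Step 3. Trace each warning in 1.3 into eligibility.**

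| Group warned about in 1.3 | Covered in 6.2 or 6.3? |
|---|---|
| Pregnant women | No |
| Nursing women | No |
| Hypersensitivity to tetracyclines | Yes, for doxycycline (in both lists) |
| Children under 8 | Yes, in effect, through the adult age limit |

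That is 2 of 4 covered and 2 of 4 not. If only the contraindication sentence is counted, leaving out the separate age warning, 1 of 3 is covered and 2 of 3 are not. The two missing groups are the same either way.

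**Step 4. Look for the safeguard elsewhere.**

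- Section 14.7 has 8 rows: criteria check, consent, OSDI, NIBUT, anterior-segment assessment, TBUT, adherence and prescribing. Rows mentioning pregnancy or nursing: 0 of 8.
- Section 7.5 restricts mineral-containing multivitamins, other antibiotics, probiotics and other topical treatments. It says nothing on pregnancy or contraception.
- Sections 7.3 and 10.1 let patients contact study staff, but that route works only once treatment has begun.
- Section 10.6 is a rule for classifying events, not for preventing them.

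**The case against.** The strongest reply is that the protocol, read as a whole, does warn the prescriber. Doxycycline is a marketed product, prescribed under 7.1 as in routine care. The investigators choose each patient's regimen themselves, without randomization (4.1). Section 1.3 tells them about the contraindication, and section 1.2 points to erythromycin or azithromycin as alternatives, particularly for women of childbearing age. Meeting the criteria obliges nobody to prescribe a contraindicated drug, and nothing in 6.2 or 6.3 says that pregnant or nursing women may enter. On this view the gap is an oversight that ordinary practice would catch.

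Part of this stands. It is an omission rather than a deliberate choice to admit these women, the sentence in 1.3 is itself correct, and a careful prescriber would probably withhold the drug. But background text and a statement about supply are not eligibility rules. The protocol did not leave every drug-related caution to the prescriber either: allergy and interfering medication were both written into the criteria. The reference to women of childbearing age in 1.2 shows that such patients were foreseeable. With no external monitoring (section 13) and no independent data monitoring (11.4), the plan has no second check on a lapse.

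A second objection concerns the remedy. A baseline exclusion does not cover conception between Visit 1 and Visit 2, and 1.3 itself says that tetracyclines may make oral contraceptives less effective. That is fair. The exclusion closes the gap at entry and does not by itself cover the treatment period.

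Consent pages are not among the text available and may carry a warning to patients. Such a warning would still not be an eligibility criterion.

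**Conclusion.** The concern holds and must be fixed. The written criteria admit two groups for whom the protocol calls the drug class contraindicated.

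The conclusion rests on the lists in 6.2 and 6.3 being complete as they appear, and nothing suggests otherwise. Eligibility belongs in the protocol, so a separate statistical analysis plan would not be expected to supply the rule. The count of groups can be argued, but the conclusion does not depend on it.

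How many of the planned 65 patients could be affected is unknown, since no expected age or sex distribution is given. The importance comes from the kind of harm and not from a number.

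**What to change.** Add one exclusion criterion to 6.3: pregnancy or breastfeeding. Confirm it at Visit 1, before prescribing, as an item within the existing criteria check in 14.7, and state how it is confirmed.

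Because this covers status at entry only, the sponsor should also consider one sentence on pregnancy during the three-month course, telling patients to report it and stop the drug, with a note on the oral contraceptive interaction described in 1.3.

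Section 4.1 mixes past and future tense. If enrolment is already complete, the equivalent step is to confirm that no pregnant or nursing patient was treated, and to report that.

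The cost is one line in 6.3, one item in a check that already exists, and slightly fewer eligible patients. The sample size and the analysis do not change.

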2. STUDY RATIONALE

Despite MGD's high prevalence and impact on the general population, we still lack a standardised medical treatment for moderate to severe MGD, especially for refractory cases.

Doxycycline's main therapeutical effect on MGD inhibits the synthesis or activation of proinflammatory mediators like MMP in the corneal epithelium. Furthermore, its antimicrobial and anti-chemotactic properties are important in the lid's microbiome regulation and are crucial to optimise the meibomian gland function (improvement of meibum fluidity and glandular secretion enhancement). However, long-term use of doxycycline can be risky due to the possibility of gastrointestinal effects. Different protocols in terms of duration and dosage have been reported for doxycycline in MGD treatment, but no clear superiority of a particular protocol has been reported. [4-5] This is why, in recent years, there has been significant interest in optimising treatment protocols with lower dosage doxycycline for better tolerability without losing the therapeutical effect. [3-4] This study compares the safety and efficacy of two daily oral doxycycline protocols for refractory meibomian gland dysfunction (MGD): LCD (low-dose continuous protocol) - 50 mg of doxycycline for three months and FPP (Full-dose pulsed protocol) - 100 mg of doxycycline for the first 15 days of the month for three months.

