4. STUDY DESIGN

4.1 Study Description

This spontaneous, prospective, non-randomized, parallel-group, phase IV study was conducted in compliance with the tenets of the Declaration of Helsinki.

All study participants were fully consented, and written informed consent was obtained.

This study included patients with refractory MGD. Refractory MGD is defined as symptomatic MGD (OSDI > 13 points) despite 2 months of first-line treatment with lacrimal substitutes 3 times per day and meibomian gland expression with warm compresses twice per day.

The study will consist of 3 visits: Visit 1(Baseline - day 0), Visit 2 (day 90 ± 5 - 3rd month), Visit 3 (day 180 ± 5 - 6 month). At each visit, patients will receive an OSDI questionnaire, NIBUT, type I Schirmer test and AS assessment, including TBUT, corneal staining (Oxford scale)

At baseline, eligible patients will be enrolled and treated with the assigned protocol. The investigators will assign the protocol (non-randomized) in a 1:1 ratio.

At Visit 2, NIBUT, TBUT, Oxford scale and OSDI improvement will be evaluated compared with Visit 1. Patients will be carefully asked about their compliance with the treatment. Patients who interrupted the treatment for adverse events or low compliance (<75% of the protocol adherence) will exit the study and be excluded from the analysis.

At Visit 3, the study population will be evaluated as done in Visit 2

The protocols in the study are the following:

- LCD (low-dose continuous protocol) - 50 mg of doxycycline for three months
- FPP (Full-dose pulsed protocol) - 100 mg of doxycycline for the first 15 days of the month for three months.

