5. STUDY ENDPOINTS

5.1 Primary endpoints

The primary endpoint of this study are:

- OSDI
- Number of patients with OSDI improvement > 7 points (clinically significant)

Clinical Trial Protocol CPDOXY1

Comparison between continuous and pulsed oral doxycycline treatment protocols for refractory meibomian gland dysfunction - 9 months follow-up prospective study

For these parameters, the changes occurring in the two groups at each visit vs baseline will be evaluated.

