7.3 Treatment Dosage, administration, and compliance

Please note the following information:

The dosage will vary depending on the treatment plan prescribed for the patient. This may involve taking 50 mg (half a tablet) daily for three months, or 100 mg (one tablet) for 15 days each month for three months.

Patients will take the medication at home without medical supervision. However, they will be able to contact the medical staff involved in the study if they have any questions or suspect any adverse events.

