11.3.1.1 Primary efficacy endpoint

Paired t-test will be used to study OSDI. Chi-square is used to study clinically significant OSDI variation

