11.3.3 Safety analysis

Chi-square is used for drop-out rates between groups

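### Both arms receive the same total dose, and the paired t-test named for OSDI gives no estimate of the difference between arms that the objectives ask about

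*Protocol*

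**What the plan says.** - **Rationale (section 2).** The protocol cites recent interest, in the field at large, in "optimising treatment protocols with lower dosage doxycycline for better tolerability without losing the therapeutical effect", and then introduces this study as a comparison of the safety and efficacy of two regimens.
- **Arms (section 4.1).** One arm is "LCD (low-dose continuous protocol) - 50 mg of doxycycline for three months". The other, FPP, is labelled full-dose and pulsed. Section 7.3 gives the intake in the two arms as "50 mg (half a tablet) daily for three months, or 100 mg (one tablet) for 15 days each month for three months".
- **Objectives (sections 3.1 and 3.2).** They ask which protocol has the greatest impact on OSDI at six months, which has the greater effect on signs, and which has the lower adverse event rate. No non-inferiority or equivalence hypothesis is stated, and no margin.
- **Primary analysis (section 11.3.1.1).** "Paired t-test will be used to study OSDI. Chi-square is used to study clinically significant OSDI variation". Section 11.3.1.2 names the paired t-test for the secondary variables too.
- **Safety analysis (section 11.3.3).** "Chi-square is used for drop-out rates between groups".
- **Sample size (section 11.2).** It is a before-after calculation on break-up time (1 sec, SD 2.3 sec, one-tailed 2.5%, 80% power) that gives 43 patients, raised to 65 for drop-out.

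**The concern.** The rationale, the objectives and the analysis address three different questions. The rationale speaks of keeping the effect at a lower dosage. The objectives ask which protocol is better. The test named for OSDI asks whether patients within an arm changed from baseline.

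Two things are at stake. First, arms labelled low-dose and full-dose, placed directly after a sentence about lower dosage, could lead a reader to take the result as evidence on dose reduction, although the total dose is the same in both. Second, two significant within-arm improvements, or a non-significant comparison between arms, could be taken as a sign that the protocols are equally effective. Neither result would support that.

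**Working it through.** **1. Total dose, from sections 4.1 and 7.3**

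- LCD: 50 mg x 90 days = 4,500 mg (4,550 to 4,600 mg if three months are counted as 91 to 92 days).
- FPP: 100 mg x 15 days x 3 months = 100 mg x 45 days = 4,500 mg.

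The arms differ in daily dose (50 versus 100 mg) and in schedule (continuous versus 15 days a month). These two features move together and the total does not, so no arm shows what happens when the total is lowered.

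**2. The protocol's own sample size, from section 11.2**

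n = ((1.960 + 0.842) x 2.3 / 1)² = 41.5, so 42 by the normal approximation. The exact t calculation gives 44, and power at n = 43 is 79.5%. The stated 43 is reproduced within rounding, but it is the number for one before-after change and not for a comparison of two arms. Since 43 / 65 = 0.66, the enrolment figure allows for about 34% drop-out.

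**3. What the same inputs give between arms**

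Assumption: the SD of 2.3 sec applies to the change in each arm. Allocation is 1:1 (section 4.1), so the arms are 32 and 33 with all 65 patients, and 21 and 22 with 43. The test is a two-sample t-test, two-sided 5%, for a true difference of 1 sec.

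SE = SD x √(1/n₁ + 1/n₂); half-width of the 95% CI = t x SE.

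| Patients | SE (sec) | t | Half-width (sec) | Power for 1 sec |
|---|---|---|---|---|
| 65 | 2.3 x 0.2481 = 0.571 | 1.998 | 1.14 | about 41% |
| 43 | 2.3 x 0.3051 = 0.702 | 2.020 | 1.42 | about 29% |

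Both half-widths exceed the 1 sec that section 11.2 calls clinically relevant. An observed difference of exactly zero would still leave a 1 sec difference in either direction inside the interval.

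**4. OSDI, the primary endpoint**

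The protocol gives no SD for OSDI, so a range of 10 to 20 points is assumed. The half-width with 65 patients is 1.998 x SD x 0.2481:

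| Assumed SD | 10 | 12 | 15 | 18 | 20 |
|---|---|---|---|---|---|
| Half-width (points) | 5.0 | 5.9 | 7.4 | 8.9 | 9.9 |

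**5. Which named tests compare arms**

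- Paired t-test (sections 11.3.1.1 and 11.3.1.2): compares each patient with their own baseline, so it gives no LCD minus FPP estimate.
- Chi-square for OSDI improvement of more than 7 points, and for drop-outs: can compare arms, but yields a p-value and not the size of the difference.

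**The case against.** Four points on the other side deserve weight.

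- **The sentence about retained effect describes interest in the field, with citations, and is not this trial's hypothesis.** This stands. A reader might infer that the trial claims non-inferiority and lacks the margin for it. The objectives do not support that: they ask which protocol is better, for which a difference test is the right type. The defect is that the test named for OSDI is not a test between arms.
- **Equal total dose is not an error, and the arm labels correctly describe the daily dose.** This also stands. The running title already calls the study a comparison of continuous and pulsed protocols. What remains is a limit on interpretation that sections 2 and 3.1 do not state.
- **Nothing in the protocol says that a non-significant result will be read as equality.** Correct. That low dose would be declared as good as full dose is an inference a reader might draw, not something the protocol plans. Nor do the documents show that a null result is the most likely one.
- **Intervals and rules for reading a null result are often left to the SAP.** This is fair where a protocol is silent. Here section 11.3 does name the test for the primary endpoint, and that test does not answer section 3.1.

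It is also tempting to turn the 7-point OSDI criterion in section 5.1 into a non-inferiority margin. That figure is a responder cut-off within a patient, and the protocol offers no justification for using it between arms. With SD 15 or more, the half-widths above exceed 7 points, so even an observed difference of zero would fail such a rule.

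**Conclusion.** The concern holds as a mismatch between rationale, objectives and analysis. On the protocol's own regimens both arms total 4,500 mg, so the trial can compare schedules, with daily dose changing alongside, but cannot inform on a lower total dose. The analysis named for OSDI gives no between-arm estimate. If arms are compared, a non-significant result at this size would be uninformative: power of about 41% (65 patients) or 29% (43 patients) for 1 sec of break-up time, and an OSDI half-width of about 5 to 10 points with 65 patients.

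The dose arithmetic needs no assumption beyond a 90-day treatment period. The break-up time figures assume that the 2.3 sec SD applies to change in each arm. The OSDI figures rest wholly on the assumed SD range and are illustrative.

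**What to change.** 1. **Sections 2 and 3.1.** Reconcile the rationale with the objectives. Describe the contrast as continuous versus pulsed schedules at equal total dose, note that daily dose differs with schedule, and draw no conclusion about reducing total dose.
2. **Section 11.3.** Report the LCD minus FPP difference in month-6 OSDI change, in the proportion improving by more than 7 points, and in drop-outs, each with a 95% CI.
3. **Interpretation.** State in advance that any claim of similarity rests on the confidence interval and not on p > 0.05. Do not add a non-inferiority rule at 7 points unless the sponsor justifies a between-arm margin.

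This costs protocol wording and interval estimates from data already being collected, with no added patients or visits and no change in treatment. The downside is that a null result may have to be reported as inconclusive.
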